1. DEMQOL

- a. A researcher will conduct a direct interview with the PWD to complete the DEMQOL. However, if the PWD is unable to respond to questions on the

DEMQOL, this measure will be collected via proxy interview (with a staff member who is familiar with the PWD). The DEMQOL is described above.

2. GDS-SF

- a. A researcher will conduct a direct interview with the PWD to complete the GDS-SF. The GDS-SF is described above.

3. NPI-NH

- a. The NPI-NH will be conducted by a researcher by interviewing a staff member who is familiar with the PWD. The NPI-NH is described above.

4. CMAI

- a. The CMAI will be conducted by a researcher by interviewing a staff member who is familiar with the PWD. The CMAI is described above.

Staff Members

Baseline Assessments

1. Only the following demographic data will be collected:

- a. Type of community
- b. Age
- c. Gender
- d. Race/ethnicity
- e. Education level
- f. Primary language
- g. Job title
- h. How long at current job
- i. How long worked in elder care / long-term care
- j. How many residents do you work with?

Intervention Period Data Collection

1. PEER Training

- a. The PEER training will be done in person and the topics to be covered include:
 - i. *What is PEER?*
 - ii. *Characteristics of a Successful Leader*
 - iii. *Using the ISH-SI-M*
 - iv. *Preparing the Environment*
 - v. *Preparing the Tablets*
 - vi. *Steps to Training a Resident to Lead Activities*
 - vii. *Tips for PEER Training and PEER Programming*

2. Pre-Post Quiz for Training

- a. A 15-item quiz will be presented to staff before and after the training to examine knowledge transfer

3. Satisfaction Questions for PEER Training

- a. Satisfaction questions will be posed to staff after they take the PEER training

4. Treatment Fidelity / Process Measures

b. The Staff Member will be invited to oversee two PEER sessions per week for 4.5 months (enough for PWD PEER participants to attend at least six PEER sessions for each of the six activity types featured on the PEER app). For each session, a Session Observation / Evaluation Form will be completed.

Session Observation / Evaluation Form

- i. The following is a full description of the Session Observation / Evaluation Form.
 1. Items that specifically apply to Staff Members are preceded with **SM***
- ii. During each session, a two-page Session Observation / Evaluation Form will be completed. Since the steps required to lead each activity type differ, distinct Session Observation / Evaluation Forms have been created for each activity type (e.g., there is a Hearthside Book Club Session Observation / Evaluation Form, a Lingo Bingo Session Observation / Evaluation Form, etc.) However, certain parts of the form remain the same for all activities, as described next.
 1. On the top of PAGE 1 of ALL Session Observation / Evaluation Forms, the following data is collected (i.e., these data are consistently collected across all activity types):
 - a. Date of session
 - b. Person filling out form (researcher)
 - c. Site
 - d. # of Leader Form for the Day
 - e. # of Residents Attended the Activity (for that session)
 - f. Topic (or HBC Story)
 - g. Session Start Time
 - h. Session End Time
 - i. Length of Session
 - j. **SM*** Staff ID (site staff member)
 - k. Resident Leader (RL) ID
 - l. Resident Player (RP) IDs (all who attended)
 2. The remainder of PAGE 1 includes items that are unique to each activity type; these items track...
 - a. the extent to which the Resident Leader (RL) *completed* each step required to facilitate that particular activity'
 - i. For steps that only occur once (e.g., say your name out loud), there are two options: YES and NO.
 - ii. For steps that occur more than once (e.g., ask someone to read the page aloud), there are three options : YES, MORE THAN $\frac{1}{2}$ OF THE TIME; YES, UP TO $\frac{1}{2}$ OF THE TIME; and NO.
 - b. **SM*** the amount of staff help needed for that step.
 - i. There are three options: NOT AT ALL, A LITTLE, AND A LOT.
 - c. To see the exact steps tracked for each activity, see the forms themselves in the Appendix.

3. On PAGE 2 of ALL Session Observation / Evaluation Forms, the following data is collected (i.e., these data are consistently collected across all activity types):

- a. Did the RL use the physical button? (YES / NO / N/A)
- b. If NO TO 16, why not?
- c. How often did the NEXT button work successfully for the RL, even if he/she had to try more than once? (whether using the on-screen button or physical button) (NOT AT ALL / UP TO ½ / MORE THAN ½ / N/A)
- d. How often did RL have to press more than once to get the NEXT button to work? (whether using the on-screen button or physical button) (NOT AT ALL / UP TO ½ / MORE THAN ½ / N/A)
- e. **SM*** How often did the STAFF member press the NEXT button for the RL? (whether using the on-screen button or physical button) (NOT AT ALL / UP TO ½ / MORE THAN ½ / N/A)
- f. **SM*** In the researcher's opinion, did the STAFF member assist the RL more than necessary? (Could the staff member allow the resident-leader more autonomy/independence in leading activity?) (YES / NO / N/A)
- g. How often did the RL have difficulty pressing the NEXT button? (whether using the on-screen button or physical button) (NOT AT ALL / UP TO ½ / MORE THAN ½ / N/A)
- h. Would you do this again sometime? (tally all participants, even if not study)
- i. Did you like the activity? (tally all participants, even if not study)
- j. Would you recommend it to others? (tally all participants, even if not study)
- k. How often did the RL read a prompt too soon? (NOT AT ALL / UP TO ½ / MORE THAN ½ / N/A)
- l. How often did the RL read a prompt too quickly for participants to understand/hear? (NOT AT ALL / UP TO ½ / MORE THAN ½ / N/A)
- m. How often did the RL read a prompt unnecessarily? (NOT AT ALL / UP TO ½ / MORE THAN ½ / N/A)
- n. How often did the RL press the next button too soon? (NOT AT ALL / UP TO ½ / MORE THAN ½ / N/A)
- o. How often did the RL seem quite confused about what to do next? (NOT AT ALL / UP TO ½ / MORE THAN ½ / N/A)
- p. **SM*** STAFF 1. Did STAFF successfully and appropriately set up the tablets? (YES / NO / N/A)
- q. **SM*** STAFF 2. Did STAFF have any difficulty using the special table (if applicable)? (YES / NO / N/A)
- r. **SM*** STAFF 3. Did the STAFF member attach the button to

the RL tablet? (YES / NO / N/A)

- s. **SM*** STAFF 4. Did the STAFF member attach the button to the RP tablets? (YES / NO / N/A)
- t. **SM*** STAFF 5. Did you enjoy this activity? (YES / NO / N/A)
- u. **SM*** STAFF 6. Do you think the residents enjoyed it? (YES / NO / N/A)
- v. **SM*** STAFF 7. Would you do it again sometime? (YES / NO / N/A)
- w. **SM*** STAFF 8. Would you recommend it to colleagues? (YES / NO / N/A)

9.0 TIMELINE AND VISIT SCHEDULE

PWD Timeline and Visit Schedule				
Assessment / Interview / Data to Collect	Screening	Baseline	Intervention Period	Post-Treatment
Informed Consent Form (Legally Authorized Representative)	X			
Initial Screening (for Basic Criteria) Via Staff Report and/or Chart Review (PWD Initial Screening Form)	X			
Document / Confirm All Diagnoses, Type of Dementia, Meds, Demographics (Chart Review Form)	X			
Initial Enrollment (if person meets basic eligibility criteria)	X			
Assent (Person with Dementia)	X			
Mini-Mental Status Exam (MMSE)	X			
I'm Still Here Skills Inventory – PEER Version (ISH-SI-PV) [if person scores below 5 on MMSE]	X			
Final Enrollment	X			
Dementia Quality of Life (DEMQOL)Geriatric Depression Scale-Short Form (GDS-SF)		X		
PEER Leader Assessment (if potential RL)		X		
Neuropsychiatric Inventory-Nursing Home (NPI-NH)		X		
Cohen-Mansfield Agitation Inventory (CMAI)		X		
Observations of PWD in Standard Activities w/ Menorah Park Engagement Scale (MPES)		X		
Session Observation / Evaluation Form (Experimental Only) Observations of PWD during PEER activities (Experimental) and Standard Activities (Control) using the MPES			X*	
DEMQOL				X
GDS-SF				X
NPI-NH				X
CMAI				X

**As noted in the first column of this table, some Intervention Period measures differ between Experimental and Control.*

Staff Participants Timeline and Visit Schedule			
Assessment / Interview / Data to Collect	Screening/ Baseline	Intervention Period	Post-Treatment
Informed Consent Form	X		
Demographics	X		
Enrollment (if eligible)	X		
PEER Training Pre-Quiz		X	
Take PEER Training Course		X	
PEER Training Post-Quiz		X	
PEER Training Satisfaction Questions		X	
Observe/Assist with PEER Session led by Researcher		X	
Session Observation / Evaluation Form		X	
Final Satisfaction / Focus Group Questions			X

10.0 VISIT PROCEDURES

PWD

Screening Procedures

INITIAL ELIGIBILITY

A researcher will confirm the following with staff at the community and/or conduct a chart review to determine **initial eligibility** by determining whether the PWD meets the following inclusion / exclusion criteria:

- e. He/she is age 55+
- f. He/she is able to read and speak English
- g. He/she is diagnosed with dementia (of any type)
- h. He/she does NOT show signs of rapid cognitive decline or physical deterioration over the last 6 months
 - i. He/she is NOT bed confined.
 - ii. He/she is NOT completely unable to communicate verbally.
 - iii. He/she is NOT cognitively and/or physically impaired to such a point that they are unable to participate in group activities.
 - iv. He/she is actively dying.
 - v. His/her health is declining so rapidly that they are going to be unable

participate in group activities in next week.

FINAL ELIGIBILITY

If the person meets the initial inclusion / exclusion criteria, a researcher will meet directly with the person with dementia and ask him/her to sign the assent form. If the resident signs the assent form, the researcher will continue to interview him/her and determine **final eligibility** by administering the Mini-Mental Status Examination (MMSE—described in detail above) and, if needed, the ISH-SI-PV (described in detail above).

- If the person scores at least 5 on the MMSE, he/she is eligible to be a RP in the study.
- If the person scores below 5 on the MMSE, the researcher will conduct the ISH-SI-PV
 - If the person scores at least 1 on the ISH-SI-PV, he/she is eligible for the study
- If the person scores at least 13 on the MMSE, he/she is eligible to be a RL in the study.
 - Final determination as to whether the PWD is appropriate to be a RL will be determined by conducting the PEER Leader Assessment. In order to be eligible to be a RL, the person must perform adequately on the PEER Leader Assessment.

Baseline Procedures

Chart Review/Interview with Staff

Researchers will collect the following data from each PWD's chart:

- Demographics (race/ethnicity, education level, marital status, and number of years living in LTC)
- All diagnoses
- Type of dementia
- All meds

Baseline Assessment

A researcher will schedule a time to work with the PWD and conduct a direct interview with him/her to complete the MMSE, ISH-SI-PV (if needed), GDS-SF, and DEMQOL. The researcher will follow standard protocol for conducting these measures and be extensively trained on how to properly use these measures. *Please note that the MMSE is not an outcome measure.*

Caregiver Interview

Researchers will interview a caregiver to obtain data related to neuropsychiatric symptoms (based upon the NPI-NH) and agitation (based upon the CMAI) exhibited by the PWD. In addition, if needed (i.e., if the PWD was unable to respond to the DEMQOL and/or GDS questions), a researcher will interview the caregiver to conduct the proxy version of the DEMQOL and/or GDS.

Observations of Standard Activities

Researchers will observe the PWD taking part in standard activities using the MPES. Multiple observations will be taken so that an average score can be calculated for baseline, standard activity programming. Researchers will follow the standard protocols for using the MPES and be extensively trained on how to properly use these measures.

Intervention Period Procedures

The PWD will be invited to participate in two PEER sessions per week for 4.5 months. The sessions will be overseen by a staff member at the nursing home or assisted living facility. The staff member will be trained on how to conduct PEER Sessions, as described earlier.

Treatment Fidelity / Process / Satisfaction Measures

Researchers will complete a Session Observation / Evaluation Form for each scheduled session, even if the session does not actually occur due to the PWD's unavailability or refusal to participate. Data collected on the Session Observation / Evaluation Form is detailed above.

There will be no Treatment Fidelity / Process Measures for Control Participants.

Observations of PEER Sessions

Researchers will observe the PWD taking part in PEER sessions using the MPES. We will aim to complete multiple observations for each activity type, so that an average score can be calculated for PEER activity programming. Researchers will follow the standard protocols for using the MPES and be extensively trained on how to properly use these measures.

Post-Treatment Procedures

Post-Treatment Assessment

A researcher will schedule a time to work with the PWD and conduct a direct interview with him/her to complete the DEMQOL and GDS-SF.

Caregiver Interview

Researchers will interview a caregiver to obtain data related to neuropsychiatric symptoms (based upon the NPI-NH) and agitation (based upon the CMAI) exhibited by PWD. In addition, if needed (i.e., if the PWD was unable to respond to the DEMQOL and/or questions), a researcher will interview the caregiver to conduct the proxy version of the DEMQOL and/or GDS.

Staff Members

Please note: staff members will only be enrolled at Experimental Sites.

Screening Procedures

Direct Interview for Eligibility Criteria

After consent is obtained from the staff member, a researcher will ask a staff member to fill out a form that confirms that he/she meets the following criteria:

- a. The Staff Member is age 18+
- b. The Staff Member is able to read and speak English
- c. The Staff Member does not only work third shift

Intervention Period Procedures

Take Training Course

Staff will take part in a live training session.

Pre-Post Training Quiz for Training Modules

Before and after taking the PEER training, the Staff Member will be presented with a 15-item quiz.

Treatment Fidelity / Process Measures

At Experimental Sites, Staff Members will be invited to oversee two PEER sessions per week for 4.5 months. At Control Sites, staff will provide standard activities / care for 4.5 months.

A Session Observation / Evaluation Form will be completed for each scheduled session, even if the session does not actually occur due to the PWD's unavailability or refusal to participate. Data collected on the Session Observation / Evaluation Form is detailed above.

Final Satisfaction Questions

Final Satisfaction Questions

A researcher will schedule a time to work with the staff member to pose final satisfaction questions to the staff member regarding the PEER training and app. The questions will consist of a combination of closed- and open-ended questions.

11.0 FOLLOW-UP

This is a low-risk study of a non-pharmacological intervention. As such, follow up is not required. The final point of contact for PWD will be the post-treatment assessment. The final point of contact for staff members will be the final satisfaction interview.

12.0 EARLY DISCONTINUATION

Participants are free to withdraw from participation in the study at any time and for any reason. If they do withdraw, we will no longer collect data on the person.

13.0 SAFETY REPORTING

For the purposes of this study, a participant is considered enrolled if they have successfully completed the screening procedure outlined above. Safety oversight of the trial is provided by the Principal Investigator (PI), [name].

After being enrolled in the study, participant safety will be monitored regularly by the PI.

Adverse Event (AE): Any unfavorable and unintended sign, symptom, or disease temporally associated with the use of a medical treatment or procedure, regardless of whether it is considered related to the medical treatment or procedure.

Serious Adverse Event (SAE): Any AE that results in any of the following outcomes:

- Death
- Life-threatening
- Event requiring inpatient hospitalization or prolongation of existing hospitalization

- Persistent or significant disability/incapacity

As this is a minimal risk psychosocial activity intervention, no AEs or SAEs are expected per NIH definitions, as none of the risks of the study will affect medical outcomes or occurrences.

- The PI will review study conduct in real time.
- The PI will review accrual, drop-outs, and protocol deviations on an annual basis.
- The PI will review AEs individually in real-time, and in aggregate on an annual basis.
- The PI will review serious SAEs in real-time.
- SAEs and specific procedure-associated AEs will be reported to the Heartland IRB when the yearly IRB report is due, unless the SAE or AE is "possibly related" or "related" to the study procedures.
 - If the SAE or AE is "possibly related" or "related" to the study procedures, the SAE or AE will be reported to the IRB within 24 hours.
 - If any SAEs occur, the PI will, with the assistance of the IRB, determine if any modifications need to be made to the study protocol and procedures. As this is a minimal risk study, this is highly unlikely.

13.1 Specification of Safety Parameters

As this is a non-medical, short duration trial with no interim measures (pre-post design), there are no lab values or test scores that fill this role. If a participant becomes extremely embarrassed or agitated during an assessment or activity, they will be redirected, and the programming will stop. If this occurs at a clinical level that then results in an AE, it will be reported to the IRB when the yearly IRB report is due.

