13.3 Reporting Procedures

SAEs and specific procedure-associated AEs are reported to the Heartland IRB when the yearly IRB report is due, unless the SAE or AE is "possibly related" or "related" to the study procedures. If the SAE or AE possibly related" or "related" to the study procedures, the SAE or AE will be reported to the IRB within 24 hours.

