13.5 Relationship To Study Intervention

All AEs will have their relationship to study participation assessed with a level of specificity appropriate to the non-pharmacological study design. The study uses the following AE attribution scale:

Not related: The AE is clearly not related to the study procedures (i.e., another cause of the event is most plausible and/or a clinically plausible temporal sequence is inconsistent with the onset of the event).

Potentially related: An event that follows a reasonable temporal sequence from the initiation of study procedures, but that could readily have been produced by a number of other factors.

Related: The AE is clearly related to the study procedures.

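### An adverse event that follows extreme embarrassment or agitation in a session is due to the IRB yearly under Protocol 13.1, but within 24 hours under 13.0 and 13.3 if it is possibly related or related

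*Protocol*

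**What the plan says.** Five parts of Protocol section 13 bear on when the IRB hears of an AE.

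- **13.1, Specification of Safety Parameters:** "If a participant becomes extremely embarrassed or agitated during an assessment or activity, they will be redirected, and the programming will stop". If the episode reaches a clinical level and becomes an AE, "it will be reported to the IRB when the yearly IRB report is due". No exception is given and 13.3 is not cited.
- **13.2:** the PI assesses and records these parameters, and the stated purpose is to inform the IRB at the yearly report. No faster route is mentioned.
- **13.0 and 13.3, Reporting Procedures:** serious adverse events (SAEs) and certain procedure-associated AEs go in the yearly report, "unless the SAE or AE is 'possibly related' or 'related' to the study procedures". In that case "the SAE or AE will be reported to the IRB within 24 hours".
- **13.5, Relationship To Study Intervention:** three levels. The lowest is "Not related: The AE is clearly not related to the study procedures", the middle one begins "Potentially related: An event that follows a reasonable temporal sequence from the initiation of study procedures", and the top level is *related*.
- **13.6:** the only expected AE listed is extreme frustration or embarrassment in the assessments or intervention, and it is listed as associated with the study procedures.

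**The concern.** The events in 13.1 are, by definition, ones that start while a study assessment or activity is under way. They are therefore among the AEs most likely to be judged connected with study procedures, and those are the events that 13.0 and 13.3 move from the yearly report to 24 hours. Yet 13.1, the provision written specifically for them, gives only the yearly time. Study staff handling such an event have two written instructions and no stated order of precedence.

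What is at stake is how soon the IRB learns of procedure-related distress in people with dementia, for whom consent is sought from a legally authorized representative. The documents describe no independent monitoring board. The IRB is the only body outside the study team that is described as receiving these reports while the trial runs, so the time at which it is told matters. No endpoint, analysis or sample size is affected.

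**Working it through.** No figure in the plan is involved and there is nothing to recompute. The check sets the reporting rules side by side and then follows one event through them.

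**Step 1. Does a 13.1 event fall under 13.0 and 13.3?** The 24-hour rule applies to AEs as well as SAEs. A 13.1 event that becomes an AE is therefore within its reach, subject only to the relatedness grade.

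**Step 2. What grade would it receive?** The middle level of 13.5 needs a reasonable temporal sequence from the start of study procedures, with other causes also plausible. An episode that begins during an assessment or activity meets the timing part. For embarrassment, 13.6 adds an explicit link to the procedures. Grading at or above the middle level is an inference, but for embarrassment a well-supported one.

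**Step 3. Which time applies at each grade?**

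| Grade under 13.5 | Time under 13.1 | Time under 13.0 and 13.3 | Result |
|---|---|---|---|
| Not related | Yearly | Yearly, if among the AEs covered | No conflict |
| Potentially related | Yearly | 24 hours if *possibly* is meant as *potentially*; the term is not literally matched otherwise | Conflict on the likely intended reading; unclear on the literal one |
| Related | Yearly | 24 hours | Direct conflict |

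**Step 4. How far apart are the two times?** Under a yearly cycle the wait runs from almost nothing, for an event just before the report, to about 12 months for an event just after one. The ceiling is 365 × 24 = 8,760 hours, against 24 hours. Protocol section 1.0 puts a participant's time in the study at about 6.5 months. Since 6.5 is less than 12, an event early in a reporting year could reach the IRB after that participant has finished.

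**Step 5. Do the trigger and the scale use the same words?** The trigger uses *possibly related* and *related*. The scale uses *not related*, *potentially related* and *related*. Only *related* is in both. *Possibly related* is not defined in the protocol, and *potentially related* is not named in the 24-hour rule.

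**Step 6. Does another provision settle it?** Section 13.7 has the PI notify the IRB of unanticipated problems, but 13.6 lists in-session embarrassment as expected, so that route does not clearly apply to it. The PI's real-time review of AEs in 13.0 is internal and is not notice to the IRB.

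**The case against.** The best defence is that section 13 should be read as a whole. 13.0 and 13.3 state a default of yearly reporting with an exception for related events, and they state it twice. 13.1 can be read as repeating the default, and nothing in it cancels the exception. A PI applying the whole section would report a related event within 24 hours. That reading is possible, but 13.1 does not state it, contains no cross-reference and is the more specific provision. 13.2 also points to the yearly report alone. The ambiguity remains.

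Several limits on the point do stand:

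- A reader might infer that every AE arising in a session has two reporting times. It does not. 13.1 covers only AEs that result from extreme embarrassment or agitation; a fall in a session, for instance, comes under 13.0 and 13.3 alone.
- A reader might equate the 13.1 events with the expected AE in 13.6. Only embarrassment is in both. Agitation is also a symptom that the trial measures at baseline with the CMAI and the NPI-NH, so agitation in a session is not automatically caused by it.
- A reader might infer that the PI is the only safety oversight besides the IRB. Section 16.3 makes the PI and the Experimental Team Leader jointly responsible for monitoring, including participant safety and accurate AE reporting, with weekly team meetings, and 13.2 has both reviewing participant data. What is absent is independent monitoring.
- The response to the participant does not wait for the IRB. 13.1 and 13.6 provide for it at the time of the event.
- The naming mismatch has one obvious solution, since the scale has a single level between *not related* and *related*. It is a secondary point.

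**Conclusion.** The point holds for AEs that result from extreme embarrassment or agitation in an assessment or activity. When such an AE is graded *related*, 13.1 and 13.0/13.3 give different IRB reporting times outright. When it is graded *potentially related*, they differ if *possibly* is taken to mean *potentially*, as it probably is, though the protocol does not say so. The gap is 24 hours against a ceiling of about a year.

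The conclusion rests on two assumptions: that many of these events would be graded at or above the middle level, and that staff might follow 13.1 as written. The documents do not support saying that the plan will delay notice by a year. That would require the event to fall just after a yearly report and 13.0 and 13.3 to be set aside.

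This is an internal inconsistency in safety reporting that should be corrected. It does not threaten the trial's results, but following 13.1 literally would delay IRB notice of a procedure-related AE, so it is more than a clerical matter.

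**What to change.** Reconcile 13.0, 13.1, 13.2, 13.3 and 13.5 so that each attribution level has one IRB reporting time. One way that needs no new rule is to replace the fixed yearly timing in 13.1 and 13.2 with a reference to the attribution-based rule already in 13.0 and 13.3. Use one name for the middle level in both the 24-hour trigger and the 13.5 scale. In the same edit, align the statement in 13.0 that no AEs are expected with the expected AE listed in 13.6.

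The cost is a wording change to the protocol and, possibly, a few more expedited reports.
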